This study will use a within subject design with oxytocin vs. oxytocin-matching placebo and yohimbine vs. yohimbine-matching placebo. The cue reactivity (CR) (opioid craving induced by personalized opioid cues) will follow the physiological symptoms (triggered by yohimbine) to isolate the stress signal associated with opioid. Eligible participants will be randomized to use intranasal oxytocin or placebo spray under double-blind conditions for 7 days. On days 5 and 7, participants will complete a session in which they receive yohimbine and one in which they receive placebo, under double-blind conditions, with the order of these conditions randomized across participants. After a two-day wash-out period, participants will receive the opposite condition within the oxytocin group (oxytocin or placebo, counterbalanced) to be administered for 7 days. On days 14 and 16, participants will complete an additional two labs where they will receive yohimbine and yohimbine matched placebo (counterbalanced). In a follow-up visit, we will complete final assessments before concluding the study (**Figure 1**).

FIGURE 1 - Pharmacological interventions during the study

Drugs and Doses Participants will receive intranasal oxytocin (40 IU) and oxytocin-matched placebo twice a day for 14 days; there will be one week of oxytocin administration and one week of placebo administration with two days of washout between the two conditions. They will receive two oral doses of yohimbine (32.4 mg) and two oral doses of yohimbine-matched placebo in the laboratory sessions.

[name] already obtained the Investigational New Drug (IND: 135570) from FDA for this study (Appendix A).

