- 2. To protect against a breach of confidentiality, all data acquired during the study will only be accessible by the research staff and used for research purposes only. All research data will be kept in a locked filing cabinet or on a password-protected computer database in the study office. Only participant code numbers will be used to identify participants. Consent forms and logs with participant's names and codes will be locked in a separate cabinet in the PI's office as an extra layer of security. All biological samples will be guarded in a similar manner. Only participant code numbers will be labeled on biological samples and will be locked in a laboratory suite. All interviews and assessments will be conducted in an interview room with a closed door to ensure participant privacy and confidentiality. The NIH Certificate of Confidentiality will protect against disclosing any identifying information/characteristics of participants in legal demands such as court orders or subpoenas. The Certificate will ensure further protection of participants' confidentiality.
- 3. To protect against issues associated with undue inducement, participants will be compensated appropriately for their time and effort. The study involves about a week of participation and given the considerable time commitment and involvement, compensating participants for their time and travel costs is appropriate and comparable to other study protocols. Those who drop out of the study early will be compensated for sessions that they completed.
- 4. To protect against issues associated with coercion, participants will be informed that participation is not required to get help treatment help with OUD. Also, we are not enrolling vulnerable populations.

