- Yohimbine: The oral dose of yohimbine for this study is based on prior studies, in particular from an ongoing study of [name] (PI and IND holder: NCT: 02243709; IND: 121984) in which yohimbine was administered to examine neuroendocrine probes in human studies. Ample data supports the safety of vohimbine to induce craving in alcohol-dependent individuals, and the safe induction of stress in PTSD veterans and gamblers. In this study, yohimbine (32.4mg), formulated by Bayview Pharmacy is administered below the therapeutic index to a dose considered unsafe (>100mg). Furthermore, yohimbine will be administered only once, during the laboratory session and under direct supervision of the study personnel. It will be given at a safety-tested dose to increase noradrenergic activity already being evaluated in psychiatric patients with clinically relevant stress conditions such as PTSD, anxiety, and depression. Finally, yohimbine's short half-life ($t_{1/2}$ = 1-2 hour) provides a transient effect. The protocol includes close monitoring of vital signs (BP, HR and MAP) and cortisol levels. [name] and/or the CADRE NP will evaluate any possible adverse effect due to yohimbine administration. In addition, we will administer the standardized CADRE assessment to determine stress and anxiety at baseline. If anxiety is higher at the end of the study we will call [name] and/or the CADRE NP to have him meet with the patient before being released. The most common side effects reported by the use of yohimbine are: an allergic reaction, irregular or fast heartbeat, confusion, dizziness, anxiety, irritability, or nervousness, tremor, headache, skin flushing and we have not encounter these effect in our ongoing trial (PI and IND holder: NCT: 02243709; IND: 121984).

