Oxytocin, Stress, Craving, Opioid Use Disorder (OSCO)

STATISTICAL ANALYSIS PLAN

[name], PhD [name] [contact]; [contact] [contact]

ORIGINAL: 2019 AUGUST 08 REVISED: 2022 MAY 05

Clinical trial registration: Clinicaltrials.gov; NCT04051619

IND/FDA: 135570, oxytocin and yohimbine (Holder: [name])

Table of Contents

Study design, setting and approval	3
Statistical analysis	3
Missing data reporting	4
References	6

Study design, setting and approval

This was a Phase 1, outpatient, randomized, double-blind, cross-over (2x2 design with oxytocin and yohimbine), placebo-controlled, human laboratory study (**Figure 1**). The trial took place at the Center for Alcohol and Addiction Studies, Brown University, Providence, RI, USA from 2019-2023. The clinical protocol was approved by the Brown University Institutional Review Board (IRB), received an FDA Investigational New Drug (IND135570), and was registered on clinicaltrials.gov (NCT04051619). The study was initiated as a between-subjects design. However, following the COVID-19 pandemic, in order to speed up recruitment, the study was changed to a within-subjects crossover design. This modification in the clinical protocol was executed following the FDA Guidance Document on Changes or Modification during conduct of Clinical Investigations ¹. After receiving approval from the Brown University IRB in November 2021, the FDA was notified in an annual progress report and the study design was updated on clinicaltrials.gov in February 2022.

Statistical analysis

For all outcomes, we utilized an intention-to-treat (ITT) approach, where participants were examined based on their *a priori* randomized protocol and received at least one dose of the study medication (oxytocin or oxytocin-matched placebo)²

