Outcomes: Primary (craving) and secondary (safety and tolerability) outcomes were assessed in realtime in the laboratory. Seven-day oxytocin administration was compared to the oxytocin-matched placebo condition during the CR procedure, in which noradrenergic activation produced by yohimbine or yohimbinematched placebo condition (2X2 design) was measured. We used Generalized Linear Model (GLM) with modelbased estimator in the covariance matrix, with medication (oxytocin/placebo) and noradrenergic activation (yohimbine/placebo) as within-subject factors. The model was specified to evaluate the effect of drug (oxytocin/placebo) by noradrenergic (vohimbine/placebo) interaction, main effect of the drug, and main effect of noradrenergic activation. Craving was assessed using the DDQ with time coded as: t_0 =relaxation, t_1 =interaction with drug paraphernalia/opioid auditory cues and t_2 =opioid use video. Safety and tolerability were assessed using: SBP, DBP, HR (vital signs), HAM-A and STAI (anxiety). The STAI y1 (state) was included as an additional safety measure for anxiety to ensure participants were not experiencing acute symptoms of anxiety within the laboratory. The STAI y2 (trait) was inserted as a covariate in the model to control for baseline anxiety level, along with stress (PSS), HPA (cortisol), and noradrenergic response (α -amylase). Time at laboratory sessions was coded as: t_0 =baseline, t_{45min} =45-min after yohimbine administration, and t_{90min} =post cue-exposure to specifically evaluate the contribution of each laboratory procedure (vohimbine and CR). Withdrawal symptoms (COWS) and AEs were assessed at specific timepoints: t_0 =pre-laboratory and t_1 =post-laboratory procedures.

Other outcomes (safety and tolerability) were measured retrospectively during the one-week outpatient setting and included the: COWS (withdrawal), anxiety (HAM-A and STAI), stress (PSS), depression (HAM-D) and AEs. The other outcomes were analyzed using ANOVA test and the number of AEs via a χ^2 test. For missing data approach, we first categorized missing data as missing completely at random (MCAR), missing at random (MAR) or missing not at random (MNAR)⁷. Analysis with GLM (using all available pairs of data to model missing values with maximum likelihood estimation) was deemed suitable for our analyses because no systematic differences existed between participants with missing data and those with complete data (MCAR)⁸.

Missing data reporting ⁹

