- 1. Amount of missing data in the dataset:
 - a. Oxytocin condition: 10% did not receive either oxytocin or placebo condition (within subject, *n*=16; between subject, *n*=4)
 - b. Yohimbine condition: 11.12% did not receive yohimbine condition (yohimbine, *n*=14; placebo, *n*=16; no yohimbine, *n*=4):

- 2. Reason for missing:
 - a. Oxytocin condition: change from between subject to within subject design
 - b. Yohimbine condition: safety concerns due to past history of cardiovascular disease and/or current hypertension (*n*=3), stroke (*n*=1)

3. Consequences:

- a. *Oxytocin condition*: no differences between participants with and without missing values except there were no subject taking methadone in the subjects with missing values.
- b. *Yohimbine condition*: no differences between participants with and without missing values except there were cardiovascular concerns in the subjects with missing values.
- 4. *Method*: GLM with MNAR using all available pairs of data to model missing values with maximum likelihood estimation
- 5. Software: IBM SPSS Statistics for Windows, version 29 (IBM Corp., Armonk, NY, USA)

All statistical analyses were performed after participants had completed their follow-up visits and the study database had been locked. The results were presented using summary statistics: number of subjects (n); mean (M); standard deviation (SD) or frequency distributions (%) and effect size was reported as Cohen's d.

All statistical procedures were performed by IBM SPSS Statistics for Windows, version 29 (IBM Corp., Armonk, NY, USA), and GraphPad Prism (v.10) was used to generate figures (La Jolla, CA, USA). All statistical tests were two-tailed, and statistical significance was accepted if an alpha value p<.05 was obtained.

References

1. FDA. Changes or modifications during the conduct of a clinical investigation; final guidance for industry and CDRH staff. 20012001.

Schulz K, Altman D, Moher D. Consolidated Standards of Reporting Trials Group CONSORT
2010 Statement: Updated Guidelines for Reporting Parallel Group Randomised Trials. Bmj.
2010;340:c332.

4. Tukey JW. The future of data analysis. The annals of mathematical statistics. 1962;33(1):1-67.

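### The risk text gives yohimbine once although the crossover gives it twice, and the SAP rests its model on MCAR although all four people without yohimbine missed it for cardiovascular or stroke reasons

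*Protocol*

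**What the plan says.** **Dosing.** Protocol Part III, section 7 states three times that yohimbine is given a single time: in the paragraph after the list of risks, in item 8 of the protections list, and in the Yohimbine bullet, which reads "Furthermore, yohimbine will be administered only once, during the laboratory session and under direct supervision of the study personnel". Item 3 of the protections list adds "The study involves about a week of participation". Section 3 of the same Part (Drugs and Doses) says of participants: "They will receive two oral doses of yohimbine (32.4 mg"), plus two matched placebo doses. The visit descriptions place one active session in each oxytocin period (Visits 3 and 4, then Visits 5 and 6), with follow-up on day 20. The SAP gives the history: "The study was initiated as a between-subjects design", changed to a within-subjects crossover after the pandemic.

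**Missing data.** Under Outcomes, the SAP calls its model suitable because "no systematic differences existed between participants with missing data and those with complete data (MCAR"). Under Missing data reporting, item 1b counts yohimbine 14, placebo 16 and no yohimbine 4, and prints 11.12%. Item 2b gives the reasons: "safety concerns due to past history of cardiovascular disease and/or current hypertension" for three people and stroke for one. Item 3b reports "no differences between participants with and without missing values except there were cardiovascular concerns in the subjects with missing values". Item 4 names the method as "GLM with MNAR using all available pairs of data to model missing values with maximum likelihood estimation".

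**The concern.** The two defects are separate, but both concern how safely yohimbine was given and how that safety is reported.

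The single-administration statement is used as a safety argument. For a crossover participant it covers one of two active doses. Together with the one-week duration, it looks like text left over from the between-subjects design.

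In the SAP, systolic and diastolic pressure and heart rate are safety outcomes. People who missed yohimbine because of hypertension, cardiovascular history or stroke were selected on something closely tied to those outcomes, so their missingness is not completely at random. It could be treated as missing at random if the deciding history were in the model. The listed covariates are trait anxiety, perceived stress, cortisol and alpha-amylase, and none of them carries it. The MNAR label does not help: maximum likelihood on all available data does not by itself handle data missing not at random, and the SAP describes no model for the missingness. At stake are the yohimbine contrast on vital signs and the population to which the yohimbine safety conclusion applies.

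**Working it through.** **1. Doses.** One active session per oxytocin period × 2 periods = 2 active doses of 32.4 mg, against one in the risk text. By the visit days the closest possible spacing is day 7 to day 14, seven days.

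**2. The SAP's printed figures.**
- Oxytocin row: 16 within-subject + 4 between-subject = 20 people; 20 × 2 conditions = 40; 4/40 = 10%, as printed.
- Yohimbine reasons: 3 + 1 = 4, matching the count without yohimbine.
- Printed 11.12%: 4/36 = 11.11% is close. A denominator of 36 arises in two ways: 16 × 2 + 4 × 1 = 36 person-periods, or (14 + 4) × 2 = 36 person-conditions.
- The listed counts sum to 14 + 16 + 4 = 34, and 4/34 = 11.76%, which does not match.

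Per person, the share without yohimbine is 4/20 = 20% (oxytocin row) or 4/18 = 22.2% (yohimbine row, 14 + 4). The SAP does not show which is right, nor how many people had both session types.

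**3. The mechanism.** The stated reason for all four is a cardiovascular or stroke history or current hypertension, and item 3b names cardiovascular concerns as the difference between the groups. Those two statements contradict MCAR without any calculation.

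**4. What bias is possible.** Suppose the four gave yohimbine-placebo sessions and no yohimbine sessions, and the contrast uses all available data. Let D be their excess pressure, ρ the within-person correlation the model uses, and take equal variances. The placebo mean is raised by 0.20 × D, but the model carries only ρ × 0.20 × D over to the yohimbine mean. The yohimbine-minus-placebo effect is then understated by

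(1 − ρ) × 0.20 × D.

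D and ρ are assumptions; the documents give neither.

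| D (mmHg) | ρ = 0 | ρ = 0.5 | ρ = 0.7 | ρ = 0.9 |
|---|---|---|---|---|
| 0 | 0 | 0 | 0 | 0 |
| 10 | 2.0 | 1.0 | 0.6 | 0.2 |
| 20 | 4.0 | 2.0 | 1.2 | 0.4 |

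With 4/18 in place of 4/20 each entry rises by the factor 0.222/0.20 = 1.11. A simulation (20,000 runs; assumed true effect 8 mmHg and SD 12) agrees: D = 10 with ρ = 0.7 gave 7.4, and D = 20 with ρ = 0.9 gave 7.6. The paired estimate returned 8.0 in both. If the four gave no yohimbine-placebo sessions, or if the contrast is already paired, this bias is zero.

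**5. Cost of pairing.** With n pairs and 20 people giving placebo sessions, the ratio of the paired to the all-available-data standard error is

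√{ [2(1 − ρ)/n] / [(1 − ρ²)/n + (1 − ρ)²/20] }.

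- n = 16, ρ = 0: √(0.125/0.1125) = 1.054; ρ = 0.9: √(0.0125/0.012375) = 1.005.
- n = 14, ρ = 0: √(0.14286/0.12143) = 1.085; ρ = 0.9: √(0.014286/0.014071) = 1.008.

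**The case against.** **On dosing.** The sentence can be read as once per session, since the visit text gives a single oral dose each time, and sections 2 and 3 of Part III state the full schedule. But the risk text speaks of one laboratory session and sits beside a one-week duration, so the leftover reading is the more natural. The statement is also not wrong for everyone: four people were between-subject, for whom the original design implies one active dose, and four had none. That stands, and the point is limited to crossover participants. A reader might infer an unsafe dose, a missing cardiovascular or second-dose rule, or misinformed participants. The documents support none of these. Each dose is 32.4 mg against an unsafe level above 100 mg, the stated half-life is 1 to 2 hours, and active doses are days apart. Clinical screening is described, and the drug attachments and consent form were not available. The trial ran from 2019 to 2023, so a correction now serves the record, not participants.

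**On missing data.** The numerical harm is conditional throughout. It needs the four to have given yohimbine-placebo sessions, to have had higher pressures, and to enter an unpaired contrast under a weak correlation structure. The reference to all available pairs may already mean a paired analysis, though the SAP does not define a pair. This objection stands against any claim of a demonstrated bias. It does not rescue the MCAR statement, which the SAP's own reporting contradicts.

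**Conclusion.** Both contradictions are in the text. The risk section understates active yohimbine exposure for crossover participants, one dose against two. The SAP's MCAR justification is contradicted by its own account of why four people had no yohimbine, and it conflicts with the MNAR label given later.

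The size of any effect on the vital-sign results cannot be established. The range in the working runs from zero to 4.0 mmHg, and the top needs both D = 20 and a model that uses no within-person correlation. A reader might take that figure as the expected error; it is an illustration on assumed inputs. The vital signs are among the safety outcomes, which the SAP's Outcomes paragraph lists as secondary, and no effect on craving has been shown. Whatever the bias, the yohimbine safety result describes only people judged fit to receive it. The wording conflicts are certain; the consequence for the estimate is not.

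**What to change.** 1. In all three places in Part III, section 7, replace the single-administration statement with *one dose in each of two periods, two in total*, and correct the one-week duration in item 3 of the protections list.
2. Drop the MCAR justification for the yohimbine data and state one mechanism consistently in both SAP sections.
3. Estimate the yohimbine effect on systolic pressure, diastolic pressure and heart rate within person, among those with both yohimbine and yohimbine-placebo sessions. Limit the yohimbine safety conclusion to patients judged fit to receive it.
4. Report the number of people with each session type and with both. Reconcile 14/16/4 and 11.12%, and state the denominator.
5. Keep the four in the Aim 2 analysis, which uses only yohimbine-placebo sessions, provided they had such sessions.

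Cost: text edits and a re-analysis of existing data, with no new participants. The standard error is about 0.5% to 5.4% larger with 16 pairs, or 0.8% to 8.5% larger with 14 pairs and 20 people on placebo, for ρ from 0.9 down to 0. The safety conclusion covers a narrower population, which is the one the data describe.

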Oxytocin, Stress, Craving, Opioid Use Disorder (OSCO)

STATISTICAL ANALYSIS PLAN

[name], PhD [name] [contact]; [contact] [contact]

ORIGINAL: 2019 AUGUST 08 REVISED: 2022 MAY 05

Clinical trial registration: Clinicaltrials.gov; NCT04051619

IND/FDA: 135570, oxytocin and yohimbine (Holder: [name])

Table of Contents

Study design, setting and approval	3
Statistical analysis	3
Missing data reporting	4
References	6

Study design, setting and approval

This was a Phase 1, outpatient, randomized, double-blind, cross-over (2x2 design with oxytocin and yohimbine), placebo-controlled, human laboratory study (**Figure 1**). The trial took place at the Center for Alcohol and Addiction Studies, Brown University, Providence, RI, USA from 2019-2023. The clinical protocol was approved by the Brown University Institutional Review Board (IRB), received an FDA Investigational New Drug (IND135570), and was registered on clinicaltrials.gov (NCT04051619). The study was initiated as a between-subjects design. However, following the COVID-19 pandemic, in order to speed up recruitment, the study was changed to a within-subjects crossover design. This modification in the clinical protocol was executed following the FDA Guidance Document on Changes or Modification during conduct of Clinical Investigations ¹. After receiving approval from the Brown University IRB in November 2021, the FDA was notified in an annual progress report and the study design was updated on clinicaltrials.gov in February 2022.

Statistical analysis

For all outcomes, we utilized an intention-to-treat (ITT) approach, where participants were examined based on their *a priori* randomized protocol and received at least one dose of the study medication (oxytocin or oxytocin-matched placebo)²

The ITT analysis was suitable for this crossover design ³ as the placebo condition was treated identically to the active drug condition (route, administration and laboratory procedures). Distributional characteristics of outcome measures were examined to evaluate similarity to the normal distribution. detailed descriptive analysis of demographics, substance use, and clinical characteristics. The cortisol had a kurtosis in excess of four; consequently, an outlier analysis was performed and a total of 5 outliers falling outside of ±3 interguartile range were Winsorized as recommended ⁴. Comparisons with these characteristics, in relation to enrolled versus completer status, were performed using *t*-tests to analyze continuous variables (age) and χ^2 for categorical variables (sex, race, medication status). Attrition rates between the screening visit and follow-up visit were examined descriptively to assess for potential bias. In addition, a logistic regression was performed to test for possible bias due to period (placebo first, then oxytocin and oxytocin first, then placebo) or medication carryover (placebo and oxytocin), as done in our prior cross-over trial ⁵. This study tested the feasibility of the combined study design, the safety and tolerability of IN oxytocin and yohimbine, and the potential value of testing IN oxytocin as adjunct therapy in an appropriately-powered larger RCT. In selecting a target sample size, we balanced power considerations and feasibility given the preliminary nature of this trial. Because of the within-subjects design, power to test the effects of the study drug was optimized for this modest sample size. For the safety and tolerability outcomes (primary) adverse events, difference was detected based on a

judgement concerning the minimal effect, which has clinical relevance in the management of patients. In a noninferiority trial, the exact sample size could not be fixed in advance because it depends upon the chosen stopping guidelines ⁶.

Outcomes: Primary (craving) and secondary (safety and tolerability) outcomes were assessed in realtime in the laboratory. Seven-day oxytocin administration was compared to the oxytocin-matched placebo condition during the CR procedure, in which noradrenergic activation produced by yohimbine or yohimbinematched placebo condition (2X2 design) was measured. We used Generalized Linear Model (GLM) with modelbased estimator in the covariance matrix, with medication (oxytocin/placebo) and noradrenergic activation (yohimbine/placebo) as within-subject factors. The model was specified to evaluate the effect of drug (oxytocin/placebo) by noradrenergic (vohimbine/placebo) interaction, main effect of the drug, and main effect of noradrenergic activation. Craving was assessed using the DDQ with time coded as: t_0 =relaxation, t_1 =interaction with drug paraphernalia/opioid auditory cues and t_2 =opioid use video. Safety and tolerability were assessed using: SBP, DBP, HR (vital signs), HAM-A and STAI (anxiety). The STAI y1 (state) was included as an additional safety measure for anxiety to ensure participants were not experiencing acute symptoms of anxiety within the laboratory. The STAI y2 (trait) was inserted as a covariate in the model to control for baseline anxiety level, along with stress (PSS), HPA (cortisol), and noradrenergic response (α -amylase). Time at laboratory sessions was coded as: t_0 =baseline, t_{45min} =45-min after yohimbine administration, and t_{90min} =post cue-exposure to specifically evaluate the contribution of each laboratory procedure (vohimbine and CR). Withdrawal symptoms (COWS) and AEs were assessed at specific timepoints: t_0 =pre-laboratory and t_1 =post-laboratory procedures.

Other outcomes (safety and tolerability) were measured retrospectively during the one-week outpatient setting and included the: COWS (withdrawal), anxiety (HAM-A and STAI), stress (PSS), depression (HAM-D) and AEs. The other outcomes were analyzed using ANOVA test and the number of AEs via a χ^2 test. For missing data approach, we first categorized missing data as missing completely at random (MCAR), missing at random (MAR) or missing not at random (MNAR)⁷. Analysis with GLM (using all available pairs of data to model missing values with maximum likelihood estimation) was deemed suitable for our analyses because no systematic differences existed between participants with missing data and those with complete data (MCAR)⁸.

Missing data reporting ⁹

- 1. Amount of missing data in the dataset:
 - a. Oxytocin condition: 10% did not receive either oxytocin or placebo condition (within subject, *n*=16; between subject, *n*=4)
 - b. Yohimbine condition: 11.12% did not receive yohimbine condition (yohimbine, *n*=14; placebo, *n*=16; no yohimbine, *n*=4):

- 2. Reason for missing:
 - a. Oxytocin condition: change from between subject to within subject design
 - b. Yohimbine condition: safety concerns due to past history of cardiovascular disease and/or current hypertension (*n*=3), stroke (*n*=1)

3. Consequences:

- a. *Oxytocin condition*: no differences between participants with and without missing values except there were no subject taking methadone in the subjects with missing values.
- b. *Yohimbine condition*: no differences between participants with and without missing values except there were cardiovascular concerns in the subjects with missing values.
- 4. *Method*: GLM with MNAR using all available pairs of data to model missing values with maximum likelihood estimation
- 5. Software: IBM SPSS Statistics for Windows, version 29 (IBM Corp., Armonk, NY, USA)

All statistical analyses were performed after participants had completed their follow-up visits and the study database had been locked. The results were presented using summary statistics: number of subjects (n); mean (M); standard deviation (SD) or frequency distributions (%) and effect size was reported as Cohen's d.

All statistical procedures were performed by IBM SPSS Statistics for Windows, version 29 (IBM Corp., Armonk, NY, USA), and GraphPad Prism (v.10) was used to generate figures (La Jolla, CA, USA). All statistical tests were two-tailed, and statistical significance was accepted if an alpha value p<.05 was obtained.

References

1. FDA. Changes or modifications during the conduct of a clinical investigation; final guidance for industry and CDRH staff. 20012001.

Schulz K, Altman D, Moher D. Consolidated Standards of Reporting Trials Group CONSORT
2010 Statement: Updated Guidelines for Reporting Parallel Group Randomised Trials. Bmj.
2010;340:c332.

4. Tukey JW. The future of data analysis. The annals of mathematical statistics. 1962;33(1):1-67.

